### **8.2.12. Date Associated with Response**

For each disease assessment after baseline, a date will be associated with the response based on collective group of disease assessments made within the protocol visit window. For complete response (CR) and partial response (PR), this will be assigned to the latest date within the disease assessments. For stable disease (SD), Non-CR/Non-PD or Not Evaluable, this will be assigned to the earliest date within the disease assessments. For PD, assign to the earliest assessment date associated with the progression.

### 8.3. Values of Potential Clinical Importance

#### 8.3.1. Laboratory Parameters

Reference ranges for all laboratory parameters collected throughout the study are provided by the laboratory. A laboratory value that is outside the reference range is considered either high abnormal (value above the upper limit of the reference range) or low abnormal (value below the lower limit of the reference range). Note: a high abnormal or low abnormal laboratory value is not necessarily of clinical concern. The laboratory reference ranges will be provided on the listings of laboratory data. Clinical laboratory test results outside of the reference range will be flagged in the listings.

To identify laboratory values of potential clinical importance, National Cancer Institute Common Terminology Criteria for Adverse Events (NCI-CTCAE v4.03 [NCI-CTCAE, 2010]) will be used to assign grades to the relevant laboratory parameters.

#### 8.3.2. Vital Signs

To identify heart rate values of potential clinical importance, NCI-CTCAE v4.03 will be used to assign categories that align with the grades for ‘Sinus bradycardia’, ‘Sinus tachycardia’, ‘Supraventricular tachycardia’, and ‘Ventricular tachycardia’.

The following criteria will be used to flag vital sign values that are values of potential clinical importance:

Vital Sign Parameter	Potential Clinical Importance (PCI) Range	Unit
Decrease from baseline Heart Rate	Decrease to <60	bpm
Increase from baseline Heart Rate	Increase to >100	bpm

To identify blood pressure values of potential clinical importance, NCI-CTCAE v4.03 will be used to assign categories that align with the grades for ‘Hypertension’.

Vital Sign Parameter	Potential Clinical Importance (PCI) Range	Unit
Increase from baseline Systolic Blood Pressure	≥120 to <140 (Grade 1) ≥140 to <160 (Grade 2) ≥160 (Grade 3)	mmHg
Increase from baseline Diastolic Blood Pressure	≥80 to <90 (Grade 1) ≥90 to <100 (Grade 2) ≥100 (Grade 3)	mmHg

Systolic blood pressure below 120 mmHg and diastolic blood pressure below 80 mmHg are considered as normal range and will receive Grade 0 designations.

To identify temperature values of potential clinical importance, NCI-CTCAE v4.03 will be used to assign categories that align with the grades for ‘Hypothermia’ and ‘Fever’.

Vital Sign Parameter	Potential Clinical Importance (PCI) Range	Unit
Increase from baseline temperature	Increase to $\geq 38$	Degrees C
Decrease from baseline temperature	Decrease to $\leq 35$	Degrees C

## **9. STUDY POPULATION ANALYSES**

Unless otherwise stated, all data listings in this section will be based on the All Treated Population.

### **9.1. Disposition of Subjects**

A listing of reasons for study withdrawal will be generated. A listing of study treatment discontinuation will be generated. The listing will include last dose date, and reasons for study treatment discontinuation.

### **9.2. Protocol Deviations**

All protocol deviations will be listed. A separated listing of inclusion/exclusion deviations will also be provided.

### **9.3. Demographic and Baseline Characteristics**

The demographic characteristics (e.g., age, sex, ethnicity, race, baseline height, and baseline weight, body mass index) will be listed.

Race and racial combinations, and family history will be listed.

Disease characteristics, as well as these medical conditions, will be presented in data listings.

Prior anti-cancer therapy will be coded using GSK Drug coding dictionary and listed. A listing of prior anti-cancer therapy will show the relationship between Anatomical Therapeutic Chemical (ATC) Level 1, Ingredient, and verbatim text.

Prior anti-cancer radiotherapy will be listed. Prior cancer and non-cancer related surgeries will be listed.

### **9.4. Treatment Compliance**

A listing of scheduled and actual treatments will be produced.

### **9.5. Concomitant Medications**

Concomitant medications will be coded using GSK Drug coding dictionary and listed. Listing for blood products or blood supportive care products will be provided.

## 9.6. Subsequent Anticancer Therapies

Follow-up anticancer therapy will be coded using GSK Drug coding dictionary. A data listing for follow up anticancer therapy will be provided.

Any follow-up anticancer surgeries will be listed.

## 10. EFFICACY ANALYSES

The evaluation of anticancer activity will be evaluated based on the All Treated Population as defined in [Section 5](#) unless otherwise specified. Since this is a Phase I study, anticancer activity will be evaluated based on clinical evidence and response criteria. Due to the very limited number of subjects, ORR was not calculated. It can be counted from the investigator assessed response listings if need.

### Lesion Assessment and Response

Lesion assessment method and timing, evaluation of disease, disease progression and response criteria will be conducted according to Response Evaluation Criteria in Solid Tumors (RECIST version 1.1) [[Eisenhauer EA](#), etc, 2009] as outlined in Appendix 8 of the protocol. Data listings for response will be provided.

### Progression-Free Survival (PFS)

PFS is defined as the interval of time (in weeks) between the start date of treatment and the earlier of the date of disease progression and the date of death due to any cause. Disease progression will be based on the assessments by the Investigator.

The date of documented disease progression will be defined as the date of disease progression based on eCRF entries. If an assessment occurs over multiple days, the earliest date of progression will be used. The date of death should be taken from the Record of Death page. Death on study due to any cause will be included.

If there is no adequate baseline assessment, the subjects will be censored at their start date of treatment. Subjects without any adequate post-baseline tumor assessments will be censored at the start date of treatment. If the subject received subsequent anti-cancer therapy prior to the date of documented events, PFS will be censored at the last adequate assessment (e.g. assessment where visit level response is CR, PR, or SD) prior to the initiation of therapy. Progressive disease (PD) will also be defined per RECIST 1.1 criteria. Otherwise, if the subject does not have a documented date of events, PFS will be censored at the date of the last adequate assessment.

Subjects who progressed or died after an extended period without adequate assessment will be censored at their date of last adequate assessment prior to progression or death even if subsequent information is available regarding progression or death. The date of response at that assessment will be used for censoring. As the assessment schedule may change through the course of the protocol, specific rules for identifying extended loss to follow-up or extended time without an adequate assessment are provided in [Section 8.2.11](#).

For subjects who receive subsequent anticancer therapy the following rules will apply:

- If the start date of the anticancer therapy is partial (i.e. either missing the day but has the month and year available or missing both day and month), the imputation rules described in [Section 8.2.5](#) will be applied. No imputation will be made for completely missing dates.

- If anticancer therapy is started without documented disease progression or is started prior to documented disease progression, then PFS will be censored at the date of the last adequate assessment that is no later than the date of initiation of anticancer therapy (i.e. if an assessment occurs on the same day as the start of new anticancer therapy the assessment will be used - as it will be assumed the assessment occurred prior to the administration of new anticancer therapy). The date of response at the last adequate assessment will be used as the censoring value.

A summary of the assignments for progression and censoring dates for PFS are specified in the following table.

Table 1. Assignments for Progression and Censoring Dates for PFS Analysis

Situation	Date of Event (Progression/Death) or Censoring	Outcome Event (Progression/Death) Or Censored
No ( or inadequate ) baseline tumor assessments and the subject has not died (if the subject has died follow the rules for death indicated at the bottom of the table)	Start Date of Treatment	Censored
No post-baseline assessments and the subject has not died (if the subject has died follow the rules for death indicated at the bottom of the table)	Start Date of Treatment	Censored
Progression documented between scheduled visits	Date of assessment of progression 	Event
No progression ( or death ) and no initiation of new anti-cancer therapy	Date of last ‘adequate’ assessment of response 	Censored
Received subsequent anti-cancer therapy prior to the date of documented events	Date of last ‘adequate’ assessment of response  ( prior to starting initiation of therapy )	Censored
Received subsequent anti-cancer therapy prior to any adequate assessment	Start Date of Treatment	Censored
Received subsequent anti-cancer therapy and no progression ( or death )	Date of last ‘adequate’ assessment of response  ( prior to starting initiation of therapy )	Censored
Death or progression after more than one missed visit	Date of last ‘adequate’ assessment of response  ( prior to missed assessments )	Censored
Death	Date of Death	Event

1. The earliest of (i) Date of radiological assessment showing new lesion (if progression is based on new lesion); or (ii) Date of radiological assessment showing unequivocal progression in non-target lesions, or (iii) Date of last radiological assessment of measured lesions (if progression is based on increase in sum of measured lesions)
2. An adequate assessment is defined as an assessment where the Investigator determined response is CR, PR, or SD.
3. If PD and New anti-cancer therapy occur on the same day assume the progression was documented first e.g., outcome is progression and the date is the date of the assessment of progression). If anti-cancer therapy is started prior to any adequate assessments, censoring date should be the start date of treatment.

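### Two PFS censoring sentences in SAP section 10 make no exception for death, contradicting the PFS definition and Table 1 (minor)

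*SAP*

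**What the plan says.** SAP section 10, Progression-Free Survival (PFS), runs the endpoint from treatment start to "the earlier of the date of disease progression and the date of death due to any cause", and adds: "Death on study due to any cause will be included".

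Two adjacent sentences in the same text then set censoring at treatment start. For baseline: "If there is no adequate baseline assessment, the subjects will be censored at their start date of treatment". For follow-up: "Subjects without any adequate post-baseline tumor assessments will be censored at the start date of treatment". Neither mentions death.

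Table 1 in that section covers the same two situations more narrowly. The baseline row reads in part "baseline tumor assessments and the subject has not died (if the subject has died follow the rules for death", and the post-baseline row begins "No post-baseline assessments and the subject has not died (if the subject has died follow the rules for death". Deaths in either situation go to the last row, where death is an event on its own date.

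Footnote 2 to Table 1 states: "An adequate assessment is defined as an assessment where the Investigator determined response is CR, PR, or SD". SAP 8.2.12 names a further response category apart from SD: "For stable disease (SD), Non-CR/Non-PD or Not Evaluable, this will be assigned to the earliest date within the disease assessments".

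**The concern.** PFS is a secondary endpoint, and Listing 51 is its planned display. A programmer who follows the prose and one who follows Table 1 would both be working to the SAP, yet for a subject who dies early they would produce different event flags and different dates. Censoring such a death at treatment start removes an event that the endpoint definition counts. With five subjects, each flag is visible to the reader of the report.

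The word 'adequate' raises two related questions. First, it is unclear whether a subject whose first scan shows progressive disease (PD) has an adequate post-baseline assessment. Second, footnote 2 has no place for the stable state of a subject with non-measurable disease only.

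**Working it through.** **Inputs.** SAP 8.2.4: a duration is stop date minus start date plus one, and days are divided by 7 to give weeks. SAP 8.2.3: the first day of treatment is study day 1 and there is no day 0. PFS in weeks is therefore study day / 7. Protocol 8.6: disease assessments every 8 weeks, with a window of 7 days either way. The first scan falls on study day 8 × 7 + 1 = 57, the second on 113 and the third on 169. All subject histories below are hypothetical, with no new anticancer therapy.

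**Step 1: deaths.** Censoring at treatment start gives 1 / 7 = 0.14 weeks.

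| Hypothetical subject | Prose | Table 1 |
|---|---|---|
| Adequate baseline, dies on day 30 before any scan | censored, 0.14 | event, 30 / 7 = 4.29 |
| Inadequate baseline, no progression, dies on day 100 | censored, 0.14 | event, 100 / 7 = 14.29 |
| Inadequate baseline, alive | censored, 0.14 | censored, 0.14 |
| No post-baseline scan, alive | censored, 0.14 | censored, 0.14 |

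The PFS definition agrees with Table 1 on both deaths. Table 1's missed-visit row does not rescue the prose. It needs more than one missed visit, no scan is due by day 30, and only the day 57 scan is due by day 100. For living subjects in the last two rows, prose and table agree.

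**Step 2: first scan shows PD.** On day 57 the PFS definition gives an event at 57 / 7 = 8.14 weeks. Across the window, days 50 to 64 give 7.14 to 9.14. If footnote 2 is carried into the post-baseline sentence, PD is not adequate and the subject is censored at 0.14. If 'adequate' there means an evaluable scan, the sentence does not apply and there is no conflict. Table 1's post-baseline row does not capture this subject, because a post-baseline assessment exists. Its only progression row, however, names progression between scheduled visits and not at one.

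**Step 3: non-measurable disease only.** Protocol 5.1, inclusion criterion 4, exempts castration-resistant prostate cancer (CRPC) from the measurable-disease requirement. Protocol Table 14 then offers CR, Non-CR/Non-PD, NE or PD, so Non-CR/Non-PD is the only stable category. An event-free subject with that result on days 57, 113 and 169 has no assessment that footnote 2 accepts. Table 1 then points to a last adequate assessment that does not exist, and the post-baseline sentence read with footnote 2 censors at 0.14. If the category counted, censoring would be at 169 / 7 = 24.14 weeks.

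**Step 4: protocol.** Protocol 11.5.2.2 censors for new anticancer therapy or where no event date is documented, and leaves further rules to the SAP. SAP 2.1 lists no change to PFS censoring. Neither supports censoring a documented death at treatment start solely for lack of an adequate scan.

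**The case against.** The best defence on deaths is that the rule is already there: the prose includes on-study deaths, and both Table 1 rows redirect them explicitly. That makes the two sentences incomplete, with the right rule beside them. It does not remove the contradiction, because the SAP introduces Table 1 as a summary and gives it no precedence. SAP 8.2 refers to separate dataset specifications that may settle the point. Those specifications, and the shell and footnotes of Listing 51, could not be seen.

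On first-scan PD the defence is stronger. Footnote 2 is attached to response cells in Table 1 and not to the prose sentence. The neighbouring phrase about an adequate baseline cannot mean CR, PR or SD, since no response exists at baseline. Reading 'adequate' in this pair as an evaluable scan is reasonable and agrees with the PFS definition. A reader might infer that the SAP definitely censors first-scan progression at treatment start; the text allows that reading but does not compel it.

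On Non-CR/Non-PD, the prose introduces its response list as an example, although footnote 2 is worded as a closed definition. The Listing 47 shell shows SD in the non-target column, so the stable non-measurable state may be recorded as SD. Protocol 8.6 calls for serial prostate specific antigen in CRPC subjects without measurable disease, while SAP 11.6 lists no such test. That suggests, without proving, that no such subject enrolled.

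**Conclusion.** The conflict over deaths stands outright and is minor. Following the prose would turn an early death from an event into a censored time of 0.14 weeks. For the baseline sentence, death is the only conflict with Table 1. A reader might infer that it also mishandles progression, but the table's baseline row makes no exception for PD either.

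The other two points are ambiguities. First-scan PD is mishandled only if footnote 2 governs the post-baseline sentence. The Non-CR/Non-PD gap matters only if a subject with non-measurable disease alone enrolled and the eCRF does not record that state as SD.

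A reader might also infer that the reported PFS data are wrong. The documents do not show this. SAP section 1 gives five enrolled subjects and listings only, so no Kaplan-Meier estimate depends on the rule. Response data (Listing 47) and deaths (Listing 31) are listed separately, so a wrong flag could be noticed. No enrolled subject is shown to have died early, progressed at a first scan or had non-measurable disease only.

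**What to change.** 1. Replace the two prose sentences with: *Subjects with no adequate baseline tumor assessment who have not died, and subjects with no evaluable post-baseline assessment, no documented PD and no death, are censored on the treatment start date; subjects who have died follow the Death row of Table 1, subject to its missed-visit and new-anticancer-therapy rows.*
2. Widen the Table 1 progression row to cover progression at, as well as between, scheduled visits.
3. In footnote 2 and the matching example in the prose, define an adequate post-baseline assessment of response as CR, PR, SD or Non-CR/Non-PD. State that this definition does not apply to baseline assessments; otherwise, read literally, no baseline scan could qualify and every living subject would be censored at treatment start. Add Non-CR/Non-PD to the Listing 47 response codes.
4. Check the PFS derivation code against the amended text.

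The cost is SAP wording, one listing footnote and a code check. No new data are needed.

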## 11. SAFETY ANALYSES

Unless otherwise specified, all the safety analyses will be based on the All Treated Population as defined in [Section 5](#).

### 11.1. Extent of Exposure

Extent of exposure to GSK2820151 will be listed. The subject's average daily dose, defined as the cumulative dose divided by the duration of exposure for each subject, will be listed.

All dose reductions and dose interruptions will be listed separately.

### 11.2. Adverse Events

AEs will be coded to the preferred term (PT) level using the Medical Dictionary for Regulatory Affairs (MedDRA dictionary version 21.1) and grouped by system organ class (SOC). AEs will be graded by the investigator according to the NCI-CTCAE v4.03.

All AEs will be listed.

### 11.3. Adverse Events of Special Interest

For any cardiovascular events detailed in Protocol Appendix 6 and all deaths, whether or not they are considered SAEs, specific Cardiovascular (CV) and Death sections of the eCRF will be required to be completed. These sections include questions regarding cardiovascular (including sudden cardiac death) and non-cardiovascular death. CV and death data will be listed separately.

### 11.4. Deaths and Serious Adverse Events (SAEs)

In the event that a subject has withdrawn consent, no data after the withdrawal of consent date from this subject including death is supposed to appear in the database, which should be part of the data cleaning process. A listing will be generated to provide subject-specific details on subjects who died.

SAEs are included in the listing of all adverse events. Separate supportive listings with subject-level details will be generated for

- Fatal SAEs
- Non-Fatal SAEs.

Primary and secondary cause of death will be presented in subject data listings.

### 11.5. Adverse Events Leading to Discontinuation of Study Treatment and/or Withdrawal from the Study and Other Significant Adverse Events

Separate AEs supportive listings will be generated with subject level details for those subjects:

- AEs leading to discontinuation of study treatment
- AEs leading to withdrawal from the study
- AEs leading to dose interruptions
- AEs leading to dose reductions

### 11.6. Clinical Laboratory Evaluations

The assessment of laboratory toxicities will examine the following laboratory tests:

**Clinical Chemistry:** Total and direct bilirubin, Aspartate aminotransferase (AST), Alanine aminotransferase (ALT), Alkaline phosphatase, Total Protein, Albumin, Sodium, Potassium, Calcium, Blood Urea Nitrogen (BUN), Creatinine, Chloride, Fasting Glucose, Ionized Calcium, Gamma-glutamyltransferase, Total carbon dioxide, Uric Acid, and Magnesium.

**Hematology:** Hemoglobin (HGB), Platelet count, Red Blood Cell (RBC) count, White Blood Cell (WBC) count, Neutrophils (Absolute), Lymphocytes (Absolute), Monocytes (Absolute), Eosinophils (Absolute), Basophils (Absolute), Neutrophils (%), Lymphocytes (%), Monocytes (%), Eosinophils (%) and Basophils (%).

**Thyroid Function Test:** Thyroid-stimulating hormone (TSH) and free thyroxine (T4 and T3) test.

**Urinalysis:** pH, Microscopic examination, Specific gravity, Ketones, Protein, Glucose, Blood.

**Coagulation Test:** Prothrombin Time, Partial Thromboplastin Time (PTT), International Normalized Ratio (INR), and Fibrinogen.

**Pancreatic Markers:** Amylase, Lipase.

**Lipid Panel:** Triglycerides, Total Cholesterol, low density lipoprotein (LDL), and high density lipoprotein (HDL).

**Serum:** Creatine Kinase (CK), Creatine Kinase-MB isoenzyme (CKMB), Troponin I, Troponin T, N-terminal pro-B-Type natriuretic peptide (NT-proBNP), Thyroid-stimulating hormone (TSH), C-Peptide, 1,5-Anhydroglucitol (1,5 AG), Hemoglobin A1C, and Insulin.

Laboratory grades will be reported, where applicable, using the Common Terminology Criteria for Adverse Events (CTCAE v4.03). Listings of laboratory data will be provided.

## 11.7. Other Safety Measures

### Vital Signs

A listing will be provided. Categories defined in [Section 8.3.2](#) will be presented in the listing as well.

### Performance Status

ECOG performance status will be listed. Change from baseline will be presented in the listing as well.

### ECG

Listings of abnormal ECG findings and a listing of ECG values will be provided.

### Left ventricular ejection fraction (LVEF)

LVEF results will be listed with subject level details including absolute change from baseline.

## 12. HEALTH OUTCOMES ANALYSES

No health outcomes analyses were planned for the study.

## 13. PHARMACOKINETIC ANALYSES

PK analysis of GSK2820151 drug concentration-time data and derivation of PK parameters will be conducted by non-compartmental methods using Phoenix WinNonlin Version 6.4 or higher under the direction of Clinical Pharmacology Modelling and Simulation (CPMS), GSK. Unless otherwise stated, all listings in this section will be based on the Pharmacokinetic population.

